Appendix 1B - BP protocol for centres with Phentolamine (China)

Intensive BP lowering group

TREATMENT PROTOCOL

INITIAL therapy

BP Target	SBP < 120 mmHg reached within 1 hours after randomisation
Monitoring	
 Continuous HR monitoring Record BP/HR q 5 mins during active treatment, then q 15 min for first hour, q 30 min for next 5 hours and then hourly to 24 h
Phentolamine (IV)	
 If SBP \geq120 mmHg and HR >55 bpm, repeat 5 mg IV push q 5 mins until target SBP reached (<120mmHg) or HR <55 bpm If HR increases by >15 bpm or is >90 bpm, add IV beta blocker
Hydralazine (IV)	
If BP persistently \geq 120 mmHg:
 
 ADD Hydralazine with a test dose: 5 mg IV bolus over 1 minute If SBP \geq 120 mmHg, repeat 5 mg IV bolus in 5 minutes If SBP still \geq120mmHg, give 10 mg IV bolus q 5 mins until target SBP reached. Increase to 20 mg bolus if required Maximum hydralazine dose = 240mg/24 hours
Glyceryl Trinitrate (Topical)	
If BP persistently \geq 120 mmHg:
 
 ADD topical glyceryl trinitrate (paste or patch) at a rate of 5-10 mg/24hour (\approx200-400 μg/hour). NB: also known as topical nitroglycerin
Continuous IV Infusions (requires ICU admission)	
If BP persistently \geq 120 mmHg:
 
 Phentolamine infusion 0.2-5 mg/minute If target still not reached, ADD infusion of hydralazine 50-150 μg/min OR glyceryl trinitrate 1-100 μg/Kg/min

MAINTENANCE therapy

BP Target	Maintenance of SBP 100-120 mmHg
Monitoring	
Once SBP is under target (confirmed by 4 readings 15 minutes apart):
 
 Record BP/HR q 30 minutes for 5 hours and then q 1 h for 18 h
IV treatment prn	
If SBP exceeds 120mmHg at any point:
 
 Give Phentolamine (5 mg) and/or hydralazine (10-20 mg) boluses. BP and HR should then be recorded 5 and 15 minutes later If SBP is 100-120mmHg, Phentolamine 5 mg (dose dependent on initial response) should be administered q 6 hours for the first 24 hours after symptom onset (total of 3 doses) If SBP \leq 100 mmHg or HR < 55 bpm, then cease treatment. If HR increases by >15 bpm or is >90 bpm, add IV beta blocker Note: phentolamine and hydralazine may be used together during the maintenance phase

Oral treatment

Start treatment by 24 hours (use nasogastric if required).

- If not contraindicated and no other drug is specifically indicated, start combination therapy of ACEI + diuretics in addition to previous anti-hypertensives

Note: Monoamine oxidase inhibitors are not recommended with this BP lowering agent and phosphodiesterase inhibitors must not be used with GTN.

Key to abbreviations: ACEI – Angiotensin converting enzyme inhibitor; BP – blood pressure; bpm – beats per minute; HR – heart rate; ICU – intensive care unit; q – every; prn – as required; $\mu\text{g}/\text{Kg}/\text{min}$ – micrograms per kilogram per minute; $\mu\text{g}/\text{min}$ – micrograms per minute.

Appendix 1C - BP protocol for centres with Labetalol

Early intensive BP lowering group

TREATMENT PROTOCOL

INITIAL therapy

BP Target	SBP < 120 mmHg reached within 1 hour after randomisation
Monitoring	
 Continuous HR monitoring Record BP/HR q 5 mins during active treatment, then q 15 min for first hour, q 30 min for next 5 hours and then hourly to 24 h
Labetalol (IV)	
 If SBP \geq 120 mmHg and HR >55 bpm, repeat 20 mg IV push q 5 mins until target SBP reached (< 120 mmHg) or HR <55 bpm; increase to 40 mg bolus if required Maximum labetalol dose: 300 mg / 24 hours
Hydralazine (IV)	
If BP persistently \geq 120 mmHg:
 
 ADD Hydralazine with a test dose: 5 mg IV bolus over 1 minute If SBP \geq 120 mmHg, repeat 5 mg IV bolus in 5 minutes If SBP still \geq 120 mmHg, give 10 mg IV bolus q 5 mins until target SBP reached. Increase to 20 mg bolus if required Maximum hydralazine dose = 240mg/24 hours
Glyceryl Trinitrate (Topical)	
If BP persistently \geq 120 mmHg:
 
 ADD topical glyceryl trinitrate (paste or patch) at a rate of 5-10 mg/24hour (\approx200-400 μg/hour). NB: also known as topical nitroglycerin
Continuous IV Infusions (requires ICU admission)	
If BP persistently \geq 120 mmHg:
 
 Labetalol infusion 2-8 mg/min to a maximum of 300 mg/24 hours (consider this if response to labetalol boluses is adequate but brief) If target still not reached, ADD infusion of hydralazine 50-150 μg/min OR glyceryl trinitrate 1-100 μg/Kg/min OR start infusion of Nicardipine 5-15 mg/hour

MAINTENANCE therapy

BP Target	Maintenance of SBP 100-120 mmHg
Monitoring	Once SBP is under target (confirmed by 4 readings 15 minutes apart): 
 Record BP/HR q 30 minutes for 5 hours and then q 1 h for 18 h.
IV treatment prn	
If SBP exceeds 120 mmHg at any point:
 
 Give Labetalol (20-40 mg) and/or hydralazine (10-20 mg) boluses. BP and HR should then be recorded 5 and 15 minutes later If SBP is 100-120 mmHg, Labetalol 10-40 mg (dose dependent on initial response) should be administered q 6 hours for the first 24 hours after symptom onset (total of 3 doses) If SBP \leq 100 mmHg or HR < 55 bpm, then cease treatment Maximum labetalol dose: 300 mg/24 hours

- **Note: labetalol and hydralazine may be used together during the maintenance phase**

Oral treatment

Start treatment by 24 hours (use nasogastric if required)

- If not contraindicated and no other drug is specifically indicated, start combination therapy of ACEI + diuretics in addition to previous anti-hypertensives

Note: Monoamine oxidase inhibitors are not recommended with labetalol and phosphodiesterase inhibitors must not be used with GTN.

Key to abbreviations: ACEI – Angiotensin converting enzyme inhibitor; BP – blood pressure; bpm – beats per minute; HR – heart rate; ICU – intensive care unit; q – every; prn – as required; $\mu\text{g}/\text{Kg}/\text{min}$ – micrograms per kilogram per minute; $\mu\text{g}/\text{min}$ – micrograms per minute.

Appendix 1D - BP protocol for centres with Hydralazine

Early intensive BP lowering group

TREATMENT PROTOCOL

INITIAL therapy

BP Target	SBP < 120 mmHg reached within 1 hour after randomisation
Monitoring	
 Continuous HR monitoring Record BP/HR q 5 mins during active treatment, then q 15 min for first hour, q 30 min for next 5 hours and then hourly to 24 h
Hydralazine (IV)	
 If BP persistently \geq 120 mmHg: ADD Hydralazine with a test dose: 5 mg IV bolus over 1 minute If SBP \geq 140mmHg, repeat 5 mg IV bolus in 5 minutes If SBP still \geq 120mmHg, give 10 mg IV bolus q 5 mins until target SBP reached Increase to 20 mg bolus if required Maximum hydralazine dose = 240mg
Metoprolol (IV)	
If BP persistently \geq 120 mmHg:
 
 ADD Metoprolol 5 mg IV bolus over 3-5 minutes, repeat 5mg bolus in 5 minutes x 2 if necessary but do NOT give if HR < 55bpm
Glyceryl Trinitrate (Topical)	
If BP persistently \geq 120 mmHg:
 
 ADD topical glyceryl trinitrate (paste or patch) at a rate of 5-10 mg/24hour (\approx200-400 μg/hour). NB: also known as topical nitroglycerin
Continuous IV Infusions (requires ICU admission)	
If BP persistently \geq 120 mmHg:
 
 Start infusion of hydralazine - 50-150 μg/min If target still not reached, ADD infusion of glyceryl trinitrate 1-100 μg/Kg/min OR start infusion of Nicardipine 5-15 mg/hour
MAINTENANCE therapy	
BP Target	Maintenance of SBP 100-120 mmHg
Monitoring	
Once SBP is under target (confirmed by 4 readings 15 minutes apart):
 
 Record BP/HR q 30 minutes for 5 hours and then q 1 h for 18 h.
IV treatment prn	
If SBP exceeds 120mmHg at any point:
 
 Give Hydralazine 10-20 mg boluses. BP and HR should then be recorded 5 and 15 minutes after each bolus If SBP is 100-120mmHg, give further Hydralazine 10-20 mg boluses (dependent on initial dose) q 6 hours for first 24 hours (total of 3 doses) If SBP \leq 100 mmHg or HR <55 bpm, then cease treatment
Oral treatment	Start treatment by 24 hours (use nasogastric if required)

- If not contraindicated and no other drug is specifically indicated, start combination therapy of ACEI + diuretics in addition to previous anti-hypertensives

Note: Monoamine oxidase inhibitors are not recommended with this BP lowering agent and phosphodiesterase inhibitors must not be used with GTN.

Key to abbreviations: ACEI – Angiotensin converting enzyme inhibitor; BP – blood pressure; bpm – beats per minute; HR – heart rate; ICU – intensive care unit; q – every; prn – as required; $\mu\text{g}/\text{Kg}/\text{min}$ – micrograms per kilogram per minute; $\mu\text{g}/\text{min}$ – micrograms per minute.

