6.7 Treatments Allocation

Attending clinicians are required to consider their level of clinical uncertainty over the balance of potential benefits and risks pertaining to the level of BP control in each particular patient. Investigators are encouraged to adhere to study protocols, provide active care, but are free to modify a patient's treatment as required according to clinical judgment.

Intensive BP lowering group

The aim is to achieve a systolic BP level of <120mmHg within 1 hour after randomisation and to maintain this BP level for the next 72 hours (or until hospital discharge or death if this should occur earlier). A standardised intravenous (i.v.) BP lowering regimen using locally available and approved i.v. BP lowering agents will be used, commenced immediately after randomisation in either the catheter lab or a high dependency area (e.g. acute stroke or neurointensive care unit) as is usual for patients receiving MT.

BP lowering will be titrated by repeat i.v. bolus or infusion, with a systolic BP of 100 mmHg being the safety threshold for cessation of therapy. It is anticipated that i.v. agents will be required for at least the first several hours in most cases but the timing of switch to oral BP lowering agents will be at the discretion of the responsible clinician according to BP control and patient status. It is also expected that i.v. therapy will continue to be required during the initiation of oral antihypertensive therapy, to maintain the systolic BP levels 100-120 mmHg.

When administering BP lowering treatment, care is required to ensure that severe hypotension is avoided in patients by checking first for potential dehydration and providing intravenous fluids.

Since the study seeks to address the impact of BP lowering and not a specific agent, and to ensure the trial result is maximally generalizable to existing routine practice, some flexibility is allowed in the use of locally available i.v. agents (e.g. urapidil, hydralazine, metoprolol, clevipipine), but all other aspects treatment are standardized across sites. Patients on prior oral BP lowering agents should have this continued if possible and antihypertensive therapy prescribed when patients are clinically stable as per guidelines for secondary stroke prevention. Investigators are encouraged to adhere to study protocols, provide active care, but are free to modify a patient's treatment as required according to clinical judgment.

I.v. treatment protocol

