17. APPENDIX

Appendix 1 - BP management protocol

Appendix 1A - BP protocol for centres with Urapidil (China)

Intensive BP lowering group	TREATMENT PROTOCOL
INITIAL therapy	
BP Target	SBP <120mmHg achieved within 1 hour after randomisation
Monitoring	
 Continuous HR monitoring Record BP/HR q 5 mins during active treatment, then q 15 min for first hour, q 30 min for next 5 hours and then hourly to 24 h
Urapidil (IV)	
 If SBP \geq 120 mmHg and HR >55 bpm, repeat 10-25 mg IV bolus q5 mins until target SBP reached (<120mmHg) or HR <55 bpm If HR increases by >15 bpm or is >90 bpm, add IV beta blocker
Hydralazine (IV)	
 Hydralazine test dose: 5 mg IV bolus over 1 minute If SBP \geq 120 mmHg, repeat 5 mg IV bolus in 5 minutes If SBP still \geq 120mmHg, give 10 mg IV bolus q 5 mins until target SBP reached Increase to 20 mg bolus if required Maximum hydralazine dose = 240mg
Glyceryl Trinitrate (topical)	
If BP persistently \geq 120 mmHg:
 
 ADD topical glyceryl trinitrate (paste or patch) at a rate of 5-10 mg/24 hour 
(\approx 200-400 μg/hour). NB: also known as topical nitroglycerin

Continuous IV Infusions (requires ICU admission)	
If BP persistently \geq 120 mmHg:
 
 Urapidil infusion 5-30 mg/hour If target still not reached ADD infusion of hydralazine 50-150 μg/min OR glyceryl trinitrate 1-100 μg/Kg/min
MAINTENANCE therapy	
BP Target	Maintenance of SBP 100-120 mmHg
Monitoring	Once SBP is under target (confirmed by 4 readings 15 minutes apart): 
 Record BP/HR q 30 minutes for 5 hours and then q 1 h for 18 h
IV treatment prn	
If SBP exceeds 120mmHg at any point:
 
 Give Urapidil (10-25 mg) and/or hydralazine (10-20 mg) boluses. BP and HR should then be recorded 5 and 15 minutes later If SBP is 100-120mmHg, Urapidil 10-25 mg (dose dependent on initial response) should be administered q 6 hours for the first 24 hours after symptom onset (total of 3 doses) If SBP \leq 100 mmHg, cease therapy If HR increases by >15 bpm or is >90 bpm, add IV beta blocker Note: urapidil and hydralazine may be used together during the maintenance phase

Oral treatment

Start treatment by 24 hours (use nasogastric if required)

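### The SBP condition for repeating the 5 mg hydralazine test dose is ≥120 mmHg in Appendices 1A, 1B and 1C but ≥140 mmHg in 1D and 1E, where it also disagrees with the lines around it

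*Protocol*

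**What the plan says.** Each of Protocol Appendices 1A to 1E sets out intensive-arm treatment for centres using a particular i.v. agent: urapidil, phentolamine, labetalol, hydralazine and clevidipine respectively. All five open with the same target, worded in Appendix 1D as "SBP < 120 mmHg reached within 1 hour after randomisation". All five contain a hydralazine row with the same order of boluses: a 5 mg test dose, a repeat of 5 mg, then 10 mg boluses, rising to 20 mg if needed.

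The repeat of 5 mg carries an SBP condition. In Appendix 1A it is SBP ≥ "120 mmHg, repeat 5 mg IV bolus in 5 minutes", and 1B and 1C agree. In Appendix 1D it is SBP ≥ "140mmHg, repeat 5 mg IV bolus in 5 minutes", and 1E agrees with 1D. The line that follows in 1D and 1E returns to 120: if SBP is still ≥ "120mmHg, give 10 mg IV bolus q 5 mins until target SBP reached".

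Protocol Section 6.7 leaves the choice of i.v. agent flexible, "but all other aspects treatment are standardized across sites". The same section also lets investigators modify treatment by clinical judgment.

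**The concern.** The drug, the bolus sequence and the target are the same in all five appendices, yet the condition for one step differs by 20 mmHg. The differing range, 120-139 mmHg, lies directly above the target. Nothing in the protocol or SAP says the difference is intended or gives a reason for it.

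Appendices 1D and 1E also do not read coherently on their own. The rows above and below the 140 mmHg line are keyed to 120 mmHg, so a clinician with a reading of, say, 130 mmHg after the test dose is above target but does not meet the condition for the next listed dose.

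What is at stake is a clear written instruction at a dosing step. Protocol Section 7.2.3 names severe hypotensive events in the intensive group as an example of what could lead to an amendment or early stopping, so whether an intermediate dose precedes a larger bolus should not be left to interpretation. Adherence is affected as well. Protocol Section 6.10.5 uses BP records to check adherence to the BP protocol, and SAP Table 17 tabulates non-compliance with the intervention. Adherence at this step cannot be judged consistently if the instruction can be read in two ways.

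**Working it through.** There is no sample size, power or error-rate figure to reproduce. The check is a line-by-line comparison of the hydralazine rows in the initial-therapy part of each appendix.

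| Line | 1A | 1B | 1C | 1D | 1E |
|---|---|---|---|---|---|
| Target SBP within 1 hour | <120 | <120 | <120 | <120 | <120 |
| Entry to the row (BP persistently) | no entry line | ≥120 | ≥120 | ≥120 | ≥120 |
| Test dose | 5 mg | 5 mg | 5 mg | 5 mg | 5 mg |
| Condition for repeating 5 mg | ≥120 | ≥120 | ≥120 | **≥140** | **≥140** |
| Condition for 10 mg boluses (SBP still) | ≥120 | ≥120 | ≥120 | ≥120 | ≥120 |

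Only one line differs in its threshold. The 140 mmHg figure stands in two separate appendices, so a text-extraction slip is unlikely.

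The lines can then be followed for a patient who has just had the test dose:

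- **SBP below 120 mmHg.** The target is met and no appendix calls for the repeat. All five agree.
- **SBP 140 mmHg or above.** All five call for a second 5 mg. They agree.
- **SBP 120-139 mmHg.** Appendices 1A-1C call for a second 5 mg. In 1D and 1E the repeat condition is not met, and the next written bolus is 10 mg.

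In the third case the literal hydralazine total after two boluses is 5 + 5 = 10 mg under 1A-1C. Under 1D or 1E, if the 10 mg step applies directly, it is 5 + 10 = 15 mg.

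Whether it does apply directly is not clear. The word *still* in that line can be read as presupposing that the repeat dose was given. On that reading, the hydralazine row of 1D or 1E has no bolus line for this patient. If *still* means only that SBP remains above target, the patient goes straight from 5 mg to 10 mg. The text does not settle which is meant.

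**The case against.** The strongest reply is that little turns on this. Treatment is directed towards the same target in every appendix, the literal difference is a single intermediate bolus, and Section 6.7 lets the clinician depart from the written steps. The appendices also differ openly elsewhere: metoprolol has a row only in 1D, and nicardipine appears only in 1C and 1D. Some variation by appendix is therefore built in, and the standardisation statement cannot be taken as absolute. A more direct conflict also sits in Appendix 1E, whose maintenance row calls for doubling clevidipine once SBP exceeds 120 mmHg and for keeping the dose at 130-140 mmHg.

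Most of this stands as a limit on the consequences. Three stronger readings that a reader might infer are not supported:

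- **That 1D and 1E tell sites to wait or give nothing at 120-139 mmHg.** No line says so. Even if the 10 mg step is taken to need a prior repeat dose, other rows still direct treatment when BP is persistently at or above 120 mmHg: metoprolol, topical glyceryl trinitrate and infusions in 1D, and topical glyceryl trinitrate and infusions in 1E. Under-treatment does not follow from the text.
- **That BP separation between the arms is reduced.** Nothing in the documents shows an effect in either direction. If the 10 mg step applies directly, the larger bolus comes sooner, which does not point to less separation.
- **That many patients are affected.** The documents do not say how many sites use 1D or 1E. Appendices 1A and 1B are labelled for China, where SAP Section 2.2 places approximately 60 sites. In 1E hydralazine is an addition to clevidipine.

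The reply does not remove the contradiction. Freedom to use judgment is not a substitute for a written step that can be followed, and the openly different steps concern which agents are listed, not the titration of the same agent in the same bolus sequence.

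**Conclusion.** The inconsistency is real and is in the current protocol text. Appendices 1D and 1E disagree with 1A, 1B and 1C on the SBP condition for repeating the 5 mg hydralazine dose, and with their own neighbouring lines and target. It concerns one titration step, a range of 120-139 mmHg, and only intensive-arm patients given hydralazine under 1D or 1E. The size of that group cannot be worked out from the documents.

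The conclusion assumes the appendices are read literally and that no separate site manual, which is not among the documents, explains the difference. Confidence is high for the mismatch itself and does not extend to any clinical consequence. The primary endpoint, sample size and analysis are untouched. It should be corrected because it is a treatment-decision threshold that sites are asked to follow. No view is taken on which threshold or dose is right.

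**What to change.** Reconcile the condition for repeating the 5 mg hydralazine dose across Appendices 1A to 1E, and with the neighbouring lines and the stated target. If the difference is intended, say so, and state which written step applies at 120-139 mmHg after the test dose, including whether the 10 mg line presupposes the repeat dose. The decision belongs to the sponsor's clinicians. The clevidipine maintenance lines in 1E could be checked in the same pass.

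The text change is small: a line in each appendix found to need it. It alters a treatment instruction, so it should go through the usual amendment route, with notice to sites and ethics committees; Protocol Section 6.4.1 gives the site principal investigator responsibility for protocol amendments to the IRB. No change to the SAP, sample size or data collection is needed.

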Appendix 1E - BP protocol for centres with Clevidipine

Early intensive BP lowering group

TREATMENT PROTOCOL

INITIAL therapy

BP Target	SBP < 120 mmHg reached within 1 hour after randomisation
Monitoring	
 Continuous HR monitoring Record BP/HR q 5 mins during active treatment, then q 15 min for first hour, q 30 min for next 5 hours and then hourly to 24 h
Clevidipine (IV) (requires ICU admission)	
If BP persistently ≥ 120mmHg:
 
 Initial Clevidipine dose: 2mg/h iv in first 1.5min If SBP≥ 120mmHg, add double dosage every 2-10min(4,8,16 until 32mg/h) Max dosage = 32mg/h
Hydralazine (IV)	
If BP persistently ≥ 120 mmHg:
 
 ADD Hydralazine with a test dose: 5 mg IV bolus over 1 minute If SBP ≥ 140mmHg, repeat 5 mg IV bolus in 5 minutes If SBP still ≥ 120mmHg, give 10 mg IV bolus q 5 mins until target SBP reached Increase to 20 mg bolus if required Maximum hydralazine dose = 240mg
Glyceryl Trinitrate (Topical)	
If BP persistently ≥ 120 mmHg:
 
 ADD topical glyceryl trinitrate (paste or patch) at a rate of 5-10 mg/24hour (≈ 200-400 μg/hour). NB: also known as topical nitroglycerin
Continuous IV Infusions (requires ICU admission)	
If BP persistently ≥ 120 mmHg:
 
 ADD infusion of hydralazine - 50-150 μg/min OR glyceryl trinitrate 1-100 μg/Kg/min
MAINTENANCE therapy	
BP Target	Maintenance of SBP 100-120 mmHg
Monitoring	Once SBP is under target (confirmed by 4 readings 15 minutes apart): 
 Record BP/HR q 30 minutes for 5 hours and then q 1 h for 18 h.
IV treatment prn	
If SBP exceeds 120mmHg at any point:
 
 DOUBLE the dose of Clevidipine every 2-10 minutes (4, 8, 16 and then maximum dose of 32 mg/hour) If SBP is 130-140mmHg, Keep the dose of Clevidipine If SBP < 120 mmHg or HR < 55 bpm, then HALVE the dose of Clevidipine every 2-10 minutes and then cease treatment If HR increases by >15 bpm or is >90 bpm, add IV beta blocker
Oral treatment	Start treatment by 24 hours (use nasogastric if required)

- If not contraindicated and no other drug is specifically indicated, start combination therapy of ACEI + diuretics in addition to previous anti-hypertensives

Note: Monoamine oxidase inhibitors are not recommended with this BP lowering agent and phosphodiesterase inhibitors must not be used with GTN.

Key to abbreviations: ACEI – Angiotensin converting enzyme inhibitor; BP – blood pressure; bpm – beats per minute; HR – heart rate; ICU – intensive care unit; q – every; prn – as required; $\mu\text{g}/\text{Kg}/\text{min}$ – micrograms per kilogram per minute; $\mu\text{g}/\text{min}$ – micrograms per minute.

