I.v. treatment protocols, based on available medications, are provided in Appendixes 1A to 1F. The i.v. treatment will be titrated against regular BP monitoring to achieve a target systolic BP range (100-120 mmHg) within 3 hours after successful reperfusion with MT. It is anticipated that i.v. control of systolic BP will be required for at least several hours.

Oral treatment protocol

The switch from i.v. to oral BP lowering treatment will be made at the discretion of the responsible physician, depending upon the control and stability of the BP and the clinical status of the patient. It is anticipated that oral treatment will be started by 24 hours.

The oral treatment protocol will also include a defined strategy for titration of treatment to achieve effective early systolic BP control once oral treatment is commenced. If the patient is unable to swallow, treatment should be administered via nasogastric tube.

For the intervention group, the goal is to maintain systolic BP levels <120 mmHg for at least 72 hours of hospital stay. If the patient is transferred to another hospital facility within 72 hours, then attempts should be made to continue therapy to achieve the systolic BP target of <120mmHg. The target systolic BP after hospital discharge remains 130/140 mmHg, as guideline-based recommendations for second stroke prevention. BP levels will be reviewed at 90 days follow-up and medication adjusted as necessary to maintain systolic BP <130/140 mmHg as per contemporary guidelines.

Control group (higher BP target)

Patients allocated to the control group will receive management of BP to maintain systolic BP 140-180mmHg. Appendix 1G outlines the protocol for control patients. For this group, the attending clinician should stop BP lowering treatment if the systolic BP is ≤ 150 mmHg in order to maintain a higher BP target level of 140-180 mmHg comparing to intensive group. The oral and i.v. agents used will be the same as in the intensive BP lowering group as detailed in Appendixes 1A to 1G. Oral antihypertensive therapy may be started at any time the treating physician feels the patient is stable. Oral therapy must be started by Day 7. The target systolic BP after hospital discharge is <130/140 mmHg, as per contemporary guideline-based recommendations for high risk cardiovascular disease patients.

Discontinuation of allocated management

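### Appendix 1E's clevidipine maintenance rules do not fit its own SBP 100-120 mmHg target: two rules collide at 130-140, on-target readings trigger a wean to cessation, and section 6.7's stop at 100 is not repeated

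*Protocol*

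**What the plan says.** The maintenance block of Appendix 1E opens with the target: "Maintenance of SBP 100-120 mmHg". Three SBP rules for the infusion follow:

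- Above 120 mmHg at any time: "DOUBLE the dose of Clevidipine every 2-10 minutes (4, 8, 16 and then maximum dose of 32 mg/hour").
- In a band above the target: "If SBP is 130-140mmHg, Keep the dose of Clevidipine".
- Below 120 mmHg, or with heart rate under 55 bpm: "then HALVE the dose of Clevidipine every 2-10 minutes and then cease treatment".

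Section 6.7 describes the intensive arm for every agent. The i.v. regimen is titrated "to achieve a target systolic BP range (100-120 mmHg"). It is expected to continue while oral drugs are started, "to maintain the systolic BP levels 100-120 mmHg". Titration may be by bolus or infusion, "with a systolic BP of 100 mmHg being the safety threshold for cessation of therapy".

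The sister appendices repeat that threshold. Appendix 1A reads, at or below the limit, "100 mmHg, cease therapy". Appendices 1B to 1D cease at SBP 100 mmHg or below, or at a heart rate under 55 bpm. Appendix 1E mentions 100 mmHg only as the lower end of the target.

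**The concern.** The trial randomises patients to a blood-pressure target, and section 6.7 sends staff to the appendices for the i.v. dosing that should produce it. For a clevidipine patient that page is Appendix 1E. Read at the bedside, it gives two incompatible instructions over one band and no instruction to hold a dose that has brought the patient to target. At 100 mmHg it prescribes a staged wean where section 6.7 prescribes cessation.

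At stake is consistent delivery of the intensive strategy in these patients, and a clear standard for judging adherence. Form E (section 6.10.5) is meant to check adherence to the BP protocol, which cannot be done cleanly against rules that contradict each other.

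**Working it through.** No sample size, power or alpha figure is involved. The check maps the 1E maintenance rules onto SBP bands, at heart rate 55 bpm or above, and compares them with the 1E target and section 6.7.

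| SBP (mmHg) | 1E maintenance rule | Position against target and section 6.7 |
|---|---|---|
| above 140 | double | above target |
| 130-140 | double and keep | above target; rules conflict |
| above 120, below 130 | double | above target |
| exactly 120 | none | top of target |
| above 100, below 120 | halve, then cease | in target; section 6.7 expects this range to be maintained |
| 100 or below | halve, then cease | section 6.7: cease |

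**Conflict at 130-140.** The doubling rule has no upper limit, so it covers all of 130-140. Treating the keep rule as an exception does not rescue it. The dose would then double at 121-129, be held at the higher 130-140, and double again above 140. The held patients would sit 130 − 120 = 10 to 140 − 120 = 20 mmHg above the target ceiling.

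**No hold on target.** The only keep-dose band lies wholly outside 100-120. Any in-target reading below 120 starts a wean that ends in stopping the drug, and the maintenance block gives no dose for restarting it. Section 6.7 expects i.v. therapy to maintain that same range.

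**The stop at 100.** Section 6.7 calls for cessation; 1E calls for halving every 2-10 minutes and does not say how many halvings come before stopping.

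For illustration only, suppose staff followed 1E rather than section 6.7, halved at once, took the 2 mg/h starting dose as the last step, and stopped one interval later:

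- From 4 mg/h: 2, then stop. One interval, 2-10 minutes.
- From 32 mg/h: 16, 8, 4, 2, then stop. Four intervals, 4 × 2 = 8 to 4 × 10 = 40 minutes.

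These are not upper bounds. One more halving, to 1 mg/h, would make the second case five intervals, 10-50 minutes. Nor are they expected values: 1E starts weaning below 120, so a patient still on 32 mg/h at 100 mmHg would have had to fall through the whole target range between readings.

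**Possible origin.** Section 4.2.3 gives 130-140 mmHg as the predecessor trial's intensive target, so carried-over text is plausible. That is an inference, and the defect does not depend on it.

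**The case against.** The strongest reply is that the intended direction can be recovered. The intensive goal is below 120 mmHg, the initial-phase rule in 1E doubles the dose at 120 or above, and the 130-140 bullet contradicts both. Reducing below 120 and doubling above it could be read as a feedback rule around the ceiling. Section 6.7's threshold at 100 mmHg is a floor and does not forbid earlier reduction of an infusion. Clevidipine requires ICU admission, section 6.7 lets clinicians alter treatment on clinical grounds, and the DSMB monitors BP differences between the groups.

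Much of this stands, and it limits the consequences. It does not repair the page. Clinical judgment permits departure from a rule but does not settle which of two contradictory rules is the protocol. A feedback rule around 120 would still need a hold band, whereas the 1E rule ends in cessation within the stated target.

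A reader might infer that clevidipine patients have no hypotension stop at all. The documents do not support that: the stop in section 6.7 expressly covers infusions and applies across the intensive arm. 1E conflicts with it and fails to repeat it, but the protocol does not lack it.

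Nor do the in-target doses in 1A to 1D show how an infusion should be held. They are scheduled intermittent boluses, so those appendices are relevant here only for the cease line.

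**Conclusion.** The point holds as an error in a dosing rule for the randomised intervention. Two incompatible rules apply at every reading from 130 to 140 mmHg, no reading from 100 to 120 mmHg has a keep-dose rule, and readings below 120 mmHg lead to cessation against section 6.7's expectation. The missing cease line at 100 mmHg carries less weight, because section 6.7 supplies it.

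This rests on the printed bullets alone. Scope is limited to patients treated under 1E, whose share the documents do not give. It may be tempting to infer a weaker blood-pressure separation or lost power, but neither that effect nor any effect on the primary odds ratio can be derived. Sample size and analysis do not change.

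**What to change.** In the maintenance block of Appendix 1E, subject to clinical sign-off:

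- Leave doubling for SBP above 120 mmHg.
- Move the keep-dose band from 130-140 to the 100-120 target, worded as above 100 and up to 120 so that 100 itself falls only under the stop rule.
- Remove the halve-then-cease trigger at SBP below 120. Retain stepwise halving as an option when SBP is falling towards 100, so that the only written choices are not full dose at 101 and an abrupt stop at 100.
- Add a line: cease at SBP 100 mmHg or below, per section 6.7.
- Leave the response to heart rate under 55 bpm to the clinical lead. 1B to 1D cease outright, 1A's maintenance bullets have no heart-rate stop, and 1E halves first, so consistency alone does not settle it.

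The cost is a short protocol appendix amendment, IRB notification (section 6.4.1 makes this the site PI's responsibility) and a letter to sites using 1E. No extra patients, procedures or analyses are needed.
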